#### 2.2.2 Recruitment of students

Volunteer medical students will be recruited through the USF Health listserv. After identifying potential volunteers, students will participate in pre-program training modules to ensure both the safety and anonymity of other participants. They will participate in an orientation meeting which will consist of information on filling out an honor code form outlining program expectation, what to do/not to do, and verification that the student is available for the entire six-week period. The Meals on Wheels Director of Programs & Partners will be present at the orientation to assist with presenting program expectations. She will be included in the recruitment and student approval process. Students will stay with the same assigned elder for the entirety of the trial.

#### 2.2.3 Randomization and allocation

Eligible and consenting participants are randomized to one of the two study groups in a 1:1 allocation ratio. A block-stratified method using the computer will be used for generation of randomization sequence. The block size will be random. The randomization sequence will be implemented centrally with one of the co-investigator ([name]) who is off site will retain the list. Once a participant is identified the primary investigator will call the off-site co-investigator for assignment. Given that the co-investigator is not on site will ensure adequate allocation concealment.

#### 2.2.4 Blinding

The following group of people will blinded:

- Study subjects: Study subjects will not be informed of their assignment.
- Outcome assessors and data analysts: Since the outcome data will be collected using a questionnaire, the possibility of interpretation does not exist. Data analysts will not be informed of the subject assignment and the coding for participant will be as group 1 or 2.

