#### Abstract

**Background:** There is a need for stronger community involvement with the elderly, specifically those with feelings of loneliness. Large proportions of elders in previous studies reported feelings of loneliness, and loneliness at advanced ages is a growing trend seen within the last thirty years despite advances in technology and social media. We propose a randomized control trial to determine the effectiveness of a volunteer-based lunch program on decreasing feelings of loneliness in elderly participants. *Methods:* Lonely elders in the community will be identified and matched with a trained medical student. Each student will bring provided lunches once a week to their elder participant's residence, and they will share lunch together for an hour once a week for six weeks. Enrollees are eligible for the study if they are over 60 years of age, speak English, have feelings of loneliness on the three-item scale, and display no cognitive impairment. The participants will be assessed pre and post intervention using the R-UCLA scale for loneliness, PHQ-9 for depressive symptoms, and GAD-7 for feelings of anxiety. Participant satisfaction will be assessed using Likert items as well as open-ended questions. Intervention group responses will be compared to responses of participants that did not receive the lunch meeting intervention. *Discussion:* Success of such a companion lunch program would provide an effective route to combat loneliness in the elderly.

**Keywords:** *Loneliness, elderly, depression, anxiety, RCT.* 

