There is a demonstrated need for intervention in this lonely, elderly population, with significant public health implications. A randomized control trial from 1999 implementing a visitor volunteer program for the elderly showed that strong community involvement increased

the participants' feelings of worth, social integration, and life satisfaction [10]. More recently, a local food delivery project in Tampa showed that weekly food delivery to an at-risk elderly population decreased participants' feelings of loneliness and increased their measured well-being over the course of two months [11]. While both pilot programs had short evaluation periods, they demonstrated the effectiveness of volunteer-based community involvement. Combining a visitor volunteer program with a food delivery service could serve to effectively combat the elderly community's feelings of loneliness and social isolation.

A local food delivery project in Tampa showed that weekly food delivery to an at-risk elderly population decreased participants' feelings of loneliness and increased their measured well-being over the course of two months [12]. Even though it demonstrated the effectiveness of volunteer-based community involvement, the project was constructed as a pretest-posttest, descriptive study using convenience sampling, and feelings of loneliness were evaluated as a secondary objective using a three-item loneliness screener. In our study, we plan to measure the effects of adding a volunteer visitor to the lunch program; that is, to see if eating meals with a medical student can decrease feelings of loneliness when compared with simply receiving meals through Meals on Wheels. Our study is designed as a randomized control trial in which seniors will be randomly assigned to two groups: paired with a medical student for lunch or not paired with a medical student while still receiving meals.

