## 2.1.1.1 Primary outcome measure

We will determine the effectiveness of a volunteer-based lunch program on decreasing feelings of loneliness in elderly participants. The full Revised-UCLA (R-UCLA) scale will be administered before and after the six-week trial period electronically using an iPad and Qualtrics software. There are 20 questions on the scale.

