## 2.1.1.2 Secondary outcome measures

We will evaluate whether a volunteer-based lunch program decreases feelings of depression in elderly participants using the patient health questionnaire-9 (PHQ-9). It will be administered before and after the six-week trial period electronically using an iPad and Qualtrics software. There are 9 questions on the questionnaire.

We will also assess whether a volunteer-based lunch program decreases anxiety symptoms in elderly participants using the generalized anxiety disorder 7-item scale (GAD-7). It will be administered before and after the six-week trial period electronically using an iPad and Qualtrics software.

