A designated investigator will contact potential participants who qualify via telephone. We will explain our goals and outline the framework of the study using an existing phone call template. Elders will be asked if they are willing to accept lunch company. If the elder is interested, the investigator will meet the elder at their residence with an iPad containing the study information, a written consent form, and pre-study assessment tools.

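### Section 2.2.4 lists the elders as blinded, but the weekly student lunch reveals the arm to them, and they report the primary outcome themselves

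*Protocol*

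**What the plan says.** Section 2.2.4 lists the groups to be blinded. Participants come first, with one sentence of support: "Study subjects will not be informed of their assignment". The second bullet, on outcome assessors and data analysts, argues: "Since the outcome data will be collected using a questionnaire, the possibility of interpretation does not exist". It adds that analysts see the arms only as group 1 or 2.

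Other sections describe what the elder experiences:

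- Abstract: a student brings lunch to the residence and "they will share lunch together for an hour once a week for six weeks".
- Section 1.0: elders are randomized to be "paired with a medical student for lunch or not paired with a medical student while still receiving meals".
- Section 2.2.1: an investigator outlines the study by telephone, and "Elders will be asked if they are willing to accept lunch company".
- Section 2.2.2: "Students will stay with the same assigned elder for the entirety of the trial".

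On outcomes, section 2.1.1.1 says of the 20-item R-UCLA that the "scale will be administered before and after the six-week trial period electronically using an iPad and Qualtrics software". Section 2.1.1.2 says the same of the PHQ-9 and of the GAD-7: "It will be administered before and after the six-week trial period electronically using an iPad and Qualtrics software". Section 2.2.5 makes clear that participants complete all three scales, that the investigator who brings the iPad is unaware of allocation, and that satisfaction items about the student are also collected on the iPad.

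**The concern.** Not telling someone their assignment blinds them only if the assignment cannot be seen. A student at the table every week can be seen, and so can the student's absence for an elder who has been asked about lunch company. Section 2.2.4 therefore claims a property that the design does not have.

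This matters because the outcome is the elder's own report. Visited elders may answer more favourably because they expect a benefit. Controls may answer less favourably because they hoped for company. The design cannot separate either response from the effect of the visits. A reader who takes both bullets of section 2.2.4 at face value would conclude that knowledge of the arm cannot influence the result. Section 3.0 plans publication of a direct comparison of the arms, so the claim could carry over into the report.

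**Working it through.** **Can the elder tell the arm?** Set the sections side by side.

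| Element | Intervention arm | Control arm | Source |
|---|---|---|---|
| Meals | Yes | Yes | 1.0 |
| Student at home, one hour weekly, six weeks | Yes, same student throughout | No | Abstract, 1.0, 2.2.2 |
| Sham or attention visit | Not applicable | None described | 1.0, 2.2 |
| Told about the study and asked about lunch company beforehand | Yes | Yes | 2.2.1 |

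A visited elder knows. An elder who agreed to company and receives none can infer it.

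**Who produces the outcome?** The elder completes the R-UCLA, PHQ-9 and GAD-7 (2.1.1.1, 2.1.1.2, 2.2.5). Masking the investigator who carries the iPad and coding the groups for analysts protect other steps. They do not act on what the respondent enters. The argument about questionnaires in 2.2.4 covers rater judgement at most.

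**The protocol's own figure.** The only design figure is 33 pairs (2.2.1: difference 0.5, SD of pair differences 1, power 0.8, alpha 0.05; two-sided is assumed here). The normal approximation gives ((1.960 + 0.842)/0.5)² = 31.4, so 32 pairs. The noncentral t gives 34, with power 0.795 at 33. The stated 33 is thus reproduced closely. The present point does not depend on it.

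**Illustration of size.** The shifts below are assumed; none comes from the documents. Take no true effect, 33 per arm (2.2.1), a two-sample t test with df = 33 + 33 − 2 = 64, two-sided 0.05, and a between-arm reporting shift of d SD. The noncentrality is d × √(33/2) = 4.062 d.

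| Assumed shift d (SD) | Noncentrality | Probability of p<0.05 |
|---|---|---|
| 0 | 0 | 0.050 |
| 0.2 | 0.812 | 0.126 |
| 0.3 | 1.219 | 0.225 |
| 0.4 | 1.625 | 0.360 |

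A simulation of 200,000 trials per value gave 0.050, 0.125, 0.223 and 0.361. The rate reaches 0.10 at d = 0.163. The figures are the same for a shift in either direction.

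The result depends on the frame. In the paired frame that the protocol uses for its sample size (33 pairs, shift in units of the SD of pair differences), shifts of 0.2 and 0.3 give about 0.20 and 0.39.

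**A smaller point on the visiting investigator.** Section 2.2.5 names the three scales first and then the satisfaction items, but does not fix that order on the iPad. Items on how the student treats the elder could reveal the arm before the scales are finished.

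**The case against.** The strongest reply is that a visit cannot be masked against no visit, and that the protocol protects what it can: allocation is held off site (2.2.3), analysts see coded groups (2.2.4), and the visiting investigator is unaware of allocation (2.2.5). Sections 2.2.5 and 4.0 also mention the pre-study survey before assignment, so baseline answers are probably given without knowledge of the arm. All of this stands, and these protections should be kept. It supports running the trial unblinded for participants; it does not support calling them blinded.

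Four narrower objections have some weight:

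- The sentence about questionnaires sits under assessors and analysts and says nothing about respondents. True, and it is faulted here only for reaching no further than rater judgement. Next to a bullet that declares participants blinded, it still gives false reassurance.
- How fully controls understand that there are two arms depends on the telephone template and consent form, which are not shown. Disappointment in controls is therefore possible, not established.
- Section 1.0 describes loneliness as a matter of perception, so part of the change from knowing one is visited may belong to the intervention. The rates above are therefore not pure false-positive rates and carry no weight beyond illustration.
- Item order is a detail of the survey build, and nothing suggests that the student items come first. It is a minor addition, and the main point does not need it.

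**Conclusion.** The point holds. Participants are described as blinded, the intervention makes that impossible, and no other section repairs it. The trial can support a conclusion only as a comparison in which participants know or can infer their arm and report the outcome themselves.

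The size of any bias is unknown. Under the assumed two-sample setting with no true effect, a reporting shift of about 0.16 SD is enough to double the 5% error rate. Whether a shift of that size would occur, and in which direction, cannot be learned from the protocol. The conclusion rests on the described visits, the absence of any described sham and the self-reported scales, not on these figures. It should be fixed, and the correction is one of description and interpretation.

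**What to change.** In section 2.2.4:

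- Delete the bullet on study subjects and state: *Participants are not blinded, because the weekly visit is visible to them; the outcomes are self-reported and the result will be interpreted as an open-label comparison.*
- In the second bullet, replace only the sentence about questionnaires with: *Fixed-response questionnaires limit rater judgement in scoring but do not remove bias from participants' knowledge of their arm. The visiting investigator is not told the allocation (2.2.5).*
- Leave the sentence on coded groups for analysts unchanged.

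In section 2.2.5, state that the satisfaction items about the student appear only after the R-UCLA, PHQ-9 and GAD-7 are complete, because they may reveal the arm to the visiting investigator.

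The cost is a few sentences and a fixed item order on the iPad; sample size and visits do not change. The design will be described less favourably. The change discloses the bias without removing it, and item order cannot stop an elder from mentioning the student aloud.

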## 2.2.5 Follow-up procedures

After providing written consent to participate in the study, the participants will be assessed further by pre-study assessment using the R-UCLA scale for loneliness, PHQ-9 for depressive symptoms, and GAD-7 for feelings of anxiety.

At six weeks following the start of the trial, participants will complete the R-UCLA scale, PHQ-9, and GAD-7 again. A designated investigator will go to each residence with an iPad containing the post-study assessment tools electronically. He or she will not know the allocation of each elder or what cohort they are in.

Satisfaction will also be assessed on the iPad using Likert items evaluating overall satisfaction (response options: yes, to some extent, no), overall quality (response options for this and subsequent items: very satisfied, satisfied, neither, dissatisfied, very dissatisfied), how medical student treats you, and how you communicate with student. Five open-ended questions will also be used to assess the level of satisfaction: overall impressions, benefits of the program, how we could improve the program, and whether they would recommend the program to others.

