# 2.2 Design

#### 2.2.1 Identification and enrollment of participants

We plan to administer an initial three-item loneliness scale to all 926 existing Meals on Wheels of Tampa participants. From that population, we aim to enroll 66 participants into the lunch program. 33 will be assigned to the intervention group and 33 to the control group.

- *Inclusion criteria* 
  - Enrollees are eligible for the study if they are over 60 years of age, speak English, have feelings of loneliness on the three-item scale, able to give written consent, and answer surveys.
- Exclusion criteria
  - o Elders who are unable to give informed consent or complete trial documentation.

We are planning a study of a continuous response variable from matched pairs of study subjects. Prior data indicate that the difference in the response of matched pairs is normally distributed with standard deviation 1. If the true difference in the mean response of matched pairs is 0.5, we will need to study 33 pairs of subjects to be able to reject the null hypothesis that this response

difference is zero with probability (power) 0.8. The Type I error probability associated with this test of this null hypothesis is 0.05.

The three-item loneliness scale will consist of the following questions: First, how often do you feel that you lack companionship? How often do you feel left out? How often do you feel isolated from others? Answers to these three questions will be in the following format: Hardly ever (1), some of the time (2), or often (3). Existing Meals on Wheels volunteers will carry envelopes with them on their meal delivery routes and deliver the envelopes to the elders along with their meals. The envelopes will contain this questionnaire, a brief description of the study, and a return envelope. The questionnaire will contain space for each elder to fill out basic identifying information and then the three questions. A score of 5 or higher will prompt the investigators to invite the elder to enroll in the study. A waiver for written consent explaining the project and why the participant has been selected will accompany the pre-screener three-item loneliness scale.

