#### 4.0 Trial Status

This the third version of the protocol written on April 25, 2018. Initial recruitment of medical students will begin on June 1, 2018 and continue till August 10, 2018 after which the students will undergo orientation (August 13, 2018). Elders will be given the three-question survey to determine eligibility from July 9th till July 13th. Eligible elders who have provided their written consent will be given a pre-trial survey and randomly assigned into the intervention or the control groups (July 30 – August 3). The trial will last from the 20th of August till the 28th of September, after which post-trial surveys will be administered to both groups starting October 8. Trial structure along with dates are illustrated in Figure 1.

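### Do the two satisfaction items about the medical student leave controls without a valid answer and undo the masking?

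*Protocol*

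**What the plan says.** Section 2.2.5 has a designated investigator visit each residence with an iPad for the post-study R-UCLA, PHQ-9 and GAD-7. Of this visitor it says: "He or she will not know the allocation of each elder or what cohort they are in". A separate paragraph then adds satisfaction, also on the iPad. There are four Likert items: overall satisfaction, overall quality, and two on "how medical student treats you, and how you communicate with student". From the quality item onward the answers are fixed as "response options for this and subsequent items: very satisfied, satisfied, neither, dissatisfied, very dissatisfied". Open-ended questions follow. No arm is named for any of these items.

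Three other places bear on the point:
- Section 1.0 describes controls as "not paired with a medical student while still receiving meals".
- Section 2.2.4 masks the analysts: "Data analysts will not be informed of the subject assignment and the coding for participant will be as group 1 or 2".
- Section 4.0 says that "post-trial surveys will be administered to both groups starting October 8".

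The primary outcome (2.1.1.1) is R-UCLA, and the secondary outcomes (2.1.1.2) are PHQ-9 and GAD-7. Satisfaction is in neither list.

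**The concern.** Read together, these sections suggest that control elders will be asked to rate a student they never met, on a scale that offers no way out. A control could skip the item or choose the neutral option, and a neutral choice would look like a real rating. No between-arm comparison of these two items would mean anything.

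The second worry is masking. Elders know whether a student came to lunch, so the visitor and the analysts are the only parties who can realistically stay unaware of allocation. A control who asks which student is meant tells the visitor the arm. Two columns that are blank or uniformly neutral for one group code, or free text that mentions a student, would tell the analysts which code is the intervention. If either happened before the main scales were collected or analysed, a safeguard the protocol promises would be weakened.

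**Working it through.** **Inputs.** Section 2.2.1 gives the sample: "we aim to enroll 66 participants into the lunch program", and "33 will be assigned to the intervention group and 33 to the control group". So 33 + 33 = 66, which agrees. Section 2.2.5 gives 4 Likert items, of which 2 name the student. Complete follow-up is assumed throughout. The sample-size calculation has no bearing on this point.

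**Reading A: all elders get all four items.**
- Likert responses: 66 × 4 = 264.
- Control responses on the student items: 33 × 2 = 66.
- Share without a valid answer: 66 / 264 = 25%, which is every control response on those two items.

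**Reading B: the student items go to intervention elders only.**
- Responses without a valid answer: 0.
- Each student column then has 33 filled cells under one group code and 33 blanks under the other. The columns would still identify the intervention code if the analysts held them before the primary analysis.

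**Which reading does the text support?** It settles neither.
- The sentence in 4.0 about surveying both groups is the main support for Reading A. In the same section the pre-trial survey is its counterpart, and 2.2.5 describes that baseline assessment as R-UCLA, PHQ-9 and GAD-7. The post-trial surveys can therefore mean those three scales alone.
- The Abstract mentions satisfaction and then says that responses will be compared between the arms. Responses there can refer to the scales, the satisfaction items or both.
- The content of the satisfaction block (treatment by the student, benefits of the program, whether to recommend it) reads as feedback on the lunch visits, which fits Reading B.

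**What must happen for the masking to suffer?**
- *Visitor.* The elder must reveal the arm through these items before completing the scales. Section 2.2.5 mentions the scales first and satisfaction afterwards, without fixing an order. The scales are questionnaires on an iPad, and 2.2.4 already relies on the questionnaire format to rule out interpretation by assessors.
- *Analysts.* The satisfaction columns must be in the coded file before the primary analysis is done. No section says they will be.

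No numerical bias on R-UCLA can be derived from any of this.

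**The case for a change.** The strongest case for a change is that which items an elder sees, and in what order, is a matter of conduct. A later analysis plan cannot make a control's rating of an absent student valid, nor re-mask a visitor. Section 2.2.5 promises a masked visitor and, in its next paragraph, adds items that only one arm can answer, apparently at the same visit. Routing alone does not protect the analysts, as Reading B shows. The remedy would also be cheap: one form order, one routing rule and one file held back.

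Part of this stands. The text is silent on arm, and if controls were given the two items their answers could be neither interpreted nor compared. Routing would indeed need to be paired with keeping those columns away from the analysts.

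It does not carry the point further. Skip logic, form order and the contents of a masked analysis file are normally settled in the survey build, the data-handling procedures or the statistical analysis plan, which is not at hand. An elder may also reveal the arm in ordinary conversation, so two extra items add only modestly to a risk that any home visit carries. The claim in 2.2.4 that the subjects themselves are blinded is a separate matter, and changing these items would not touch it.

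**Conclusion.** No change to the plan is called for. The protocol leaves a gap: it does not say which arm receives the two student items. Anyone building the survey would see that a control has no student to rate, and nothing in the document prevents routing, asking the scales first, or holding the satisfaction data back.

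The affected share is between 0 and 66 of 264 Likert responses (0% to 25%), depending on the reading and assuming that all 66 elders are followed up. Those responses belong to items that are neither primary nor secondary outcomes. Any effect on the self-reported R-UCLA is probably small, and none has been shown. The risk to masking rests on an order of forms or an early release of data that the document does not state. The main comparison would stand if the plan were followed as written. The conclusion would need another look only if the survey as built gave controls the student items ahead of the three scales, or if the analysts received those columns before the primary analysis.
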